10.1. Intervention group (eDIAMOND)

Participants randomised to the intervention group will receive an email informing them they have been assigned to the intervention group, and that their contact information (name, phone number and email) has been securely passed to the eDIAMOND provider (Reed Wellbeing) who will contact them via email or phone (depending on the participant preferences) to process the programme onboarding and account creation. Reed Wellbeing are commissioned by the NHS to deliver weight loss and diabetes education programmes and the staff that deliver the remote coaching have a Level 3 qualification in health improvement/nutrition or similar, and have received additional training in behaviour change from Reed Wellbeing in addition to a half-day workshop on how to deliver eDIAMOND by the study team. The provider will contact the participant with information how to find and access the remote intervention which will be on a webpage. The provider will attempt to contact the participant on 3 occasions and if there is no response this would be flagged to the GP and the GP will be asked to make contact.

Participants randomised to the intervention group will receive the online support from the new programme (eDIAMOND) as well as their standard NHS diabetes care.

The intervention will involve diet, activity and behaviour change components based on key effective dietary and behaviour change components of the original DIAMOND programme. The interventions are designed to adhere to the following standards:

- The core principles are:
 - advice to exclude sugary and starchy foods high in carbohydrates (eg, biscuits, confectionery, bread, pasta, potatoes) entirely from their diet (with the exception of dairy and limited fruit intake).
 - Strict portion control and avoiding energy-dense foods.
 - Standardised 'healthy eating' advice regarding fresh vegetables, and lean meat and fish, is also included.
- Dietary specifications:
 - 800-900kcal per day during the weight loss phase.
 - <26%kcal from carbohydrates during the weight loss phase some flexibility allowed during weight maintenance to encourage long-term adherence but encourage aiming for lower carbohydrate and higher protein for satiety and weight maintenance.
 - Encourage focus on lean high protein foods and non-starchy vegetables to replace carbohydrate.
- The behaviour change component will include elements of:
 - o Goal setting
 - Self-monitoring
 - o Peer support

Self-monitoring will be supported by provision of blood pressure and blood glucose monitors for participants to use at home throughout the intervention period. The blood pressure and blood glucose monitors will be sent out via post to participants in the intervention arm following randomisation. These monitors form a key tool for participants to learn and monitor how their weight and diet affect their blood glucose and blood pressure, and will assist their clinicians in assessing their response to the programme and any medication changes. Participants will be given access to a set of instructions as part of the online materials (appendix B) (signposted to by the programme coach) and a printed copy of these sent with the equipment via post, which detail how to use the monitors, and how to interpret the readings should they be unexpectedly high or low, with a traffic light system detailing what action they should take and when they should contact their clinician. Participants will be encouraged to monitor their blood pressure 3 times per week, their blood glucose three times per week (twice a day on these days – once on waking, and once after they have eaten a meal), and to weigh themselves once a week. The coach will ask about the blood pressure, glucose and weight measures during the coaching sessions and these will form a key part of motivating and guiding participants with the intervention.

The programme will include remote coaching sessions at baseline, 2, 4, 8, 12, 16 and 20 weeks to provide support and guidance to the patient to enable them to follow the low-carbohydrate, low-energy intervention (Intervention content shown in appendix B). The participant will receive a text or phone call (depending on the method of contact the participant requests) to organise and schedule the first baseline appointment. All subsequent appointments will be remote and will also be arranged between participants and coach at a day and time convenient for both. In addition, the intervention providers are able to provide additional functionality within their digital offering including access to educational materials, recipe and cooking guides etc (Appendix B). All sessions will be audio-recorded.

Participants randomised to the intervention group will also receive 1 additional telephone appointment with their GP or practice nurse, towards the start of the 12-week intervention period, to review their current medications and assess any changes to their medication regime may be warranted in view of their anticipated participation in the programme and planned weight loss. We will encourage clinicians to do their best to make contact with participants, as this is an important patient contact – they will follow their usual practice protocols for this but we will encourage them to use at least two different methods of attempted contact out of texting, calling, emailing and writing to the patients, and on at least 3 separate occasions. We will provide clinicians with current best practice guidelines they may wish to consider but the decisions for individual patients will remain with their clinician.

For participants in the intervention group, data on participant engagement with the intervention website will be received from the company, Reed Wellbeing, and entered into the database under appropriate agreements.

Clinical responsibility for the participants will remain with the GP at all times. The GP will have access to the eCRF where the hub coach will enter session data, which will include recordings of glucose and blood pressure readings. Furthermore, the eCRF prompts the hub coach to instruct the participant on appropriate action depending on their results, which can include immediately contact the GP practice. In addition, there will be two-way communication between the hub coach and the GP practice. If any information arises in the session where hub coach deems it necessary to inform the GP, they will have details to contact the GP. The participant will be made aware that the GP is able to review any details entered and will be contacted should the need arise.

Reed Wellbeing will retain participant data for up to 12 months after participant completion of the intervention. This is to allow all data to be collected and transferred to the study team for analysis. Reed Wellbeing will not complete analysis on any participant data, and will not be permitted to use this data for any purpose outside of the trial.

10.2 Control group (NHS usual care)

Participants randomised to the control group will receive no additional intervention, and will continue to receive their usual NHS diabetes care from their general practice

10.3 Follow-Up Assessments

10.3.1 12 week-assessment

At 12 weeks after randomisation, all participants from both groups will be sent a link either via email or text to complete a food intake questionnaire.

10.3.2 20 week assessment

At 20 weeks after randomisation, all participants from both groups will also return to their GP practice for measurement of weight and blood pressure, and a blood sample will be taken (approximately 9mls) for measuring HbA1c and lipid profile (total cholesterol, LDL-cholesterol, HDL, triglycerides). To organise this visit, the participant will receive an email, text or phone call. Participants will be able to keep the blood

pressure and glucose monitors. However, if they wish to continue using the glucose monitors, they will need to purchase their own strips. If they don't wish to keep the monitors they can return them to their GP practice at their next study appointment.

At 20 weeks after randomisation, all participants from both groups will be asked by text, phone or email to complete the same questionnaires that were completed at baseline, namely: Problem Areas in Diabetes (PAID) score and the WHO 5 (quality of life assessment). They will also complete the final food intake questionnaire.

Participants in the intervention group will also be asked to complete an online questionnaire about their experience of the intervention. This questionnaire will be sent to participants via an email link to complete at home.

10.4 Sample Handling

Blood samples for 2 sets of tests (HbA1c and lipid profile (total cholesterol, LDL-cholesterol, HDL, triglycerides)) will be taken from all participants from both groups, at the 2 specified visits at their GP practice (baseline and 20 weeks), with an approximate maximum total volume of 9ml. All blood samples will be taken, handled, analysed and disposed of according to standard NHS procedures and local practice policy. The samples will be sent to NHS laboratories for analysis and results reported to the GP following standard procedures. Blood samples will not be stored after analysis.

10.5 Qualitative interviews in the intervention arm

We aim to assess the impact of the programme on the everyday lives of participants randomised to the eDIAMOND programme and how they report the support they had and its impact on their behaviour. Purposive sampling will be used to achieve maximum variation in demographic characteristics including age, gender, ethnicity and socioeconomic status, GP practice, and where data is available, weight loss outcomes, and any other characteristics that are found to be important during the interview and analysis process.

We will ask all participants to consent to interview at baseline, but this will be optional, and will contact to arrange interview only with those who agreed. A researcher will contact the participant by text message or telephone to arrange an interview after they have completed the 20 week intervention. Telephone interviews will be conducted lasting up to 60 minutes, covering the impact of the programme, their reactions to the behavioural support programme, and the ways that their behaviour has or has not changed, and their views of the impact of the programme. If the participant can only commit to a shorter time, we will offer alternative times to contact them in case this suits their schedule better; if they only have a shorter window of availability we will still endeavour to speak with them for the time that they do have available in order not to bias the sample against particular participant demographics e.g. working age participants who may have less availability but provide a valuable perspective on their experiences of the programme. All telephone interviews will be audio-recorded with prior participant consent.

The semi-structured interviews will follow broad topic areas based on the study objectives, but will encourage participants to discuss their opinions and experiences freely and in depth and confidentially.

Topics will include: their reported experience and impact of the intervention, how the support was experienced, and barriers and facilitators to engagement with the programme, including specific considerations of a remotely supported digitally-accessed intervention in terms of accessibility.

We anticipate that a sample of around 12 participants should hold sufficient information power to meet the defined qualitative study objectives, but will review the information power of the data throughout data collection and analysis and adapt the sample if needed.

For further details on data recording and record keeping for telephone interviews, please refer to Section 13.3

10.6 Fidelity Assessment

Intervention sessions delivered by the health coaches at Reed Wellbeing will be audio recorded on to Reed Wellbeing's call-recording system. These calls will be transferred via OneDrive to the study team who will analyse the conversations to ensure the intervention is being delivered as designed. The analysis of these sessions will also be used to guide additional training for health coaches, as and when required.

10.7 Early Discontinuation/Withdrawal of Participants

Each participant has the right to withdraw from the trial at any time without having to give a reason.

During the course of the study a participant may choose to withdraw early from the study treatment at any time. This may happen for several reasons, including but not limited to:

- The occurrence of what the participant perceives as an intolerable AE.
- Inability to comply with study procedures
- Participant decision

Participants may choose to stop treatment and/or study assessments but may remain on study follow-up – they will have the same opportunity to attend the study follow up appointment at their GP practice as participants who continue in the study. If we or the health coaches are informed that a participant has decided to stop participating in the intervention more than 2 weeks before their follow up appointment at the GP surgery is due, we will inform the GP practice of this via email in case their clinician wishes to review their medication with them (e.g., to restart medication they may have stopped – this will be at the clinician's discretion).

Participants may also withdraw their consent, meaning that they wish to withdraw from the study completely. If a participant decides to withdraw from treatment, we will seek to retain them in the trial for follow-up by explaining the value to the trial of collecting follow up data from all participants by speaking with the participants. However, if the participant wishes to withdraw from follow up we will use their data up to the point that they withdraw unless they request that we do not do so. The reason for withdrawal will be recorded in the electronic case report form (eCRF).

Participants who withdraw from the trial will not be replaced. Should a participant wish to withdraw, their information held with Reed Wellbeing will be retained for 12 months following cease of use to allow the study team to analyse the performance of the programme. This relates to information provided to Reed Wellbeing by the study team and the participant. Cease of use refers to the last login to the online programme by the participant. Each participant can request that their personal information retained by Reed Wellbeing is deleted by contacting the study team, who will process that request.

In addition, the Investigator may discontinue a participant from the study treatment at any time if the Investigator considers it necessary for any reason including, but not limited to:

- Pregnancy
- Ineligibility (either arising during the study or retrospectively having been overlooked at screening)
- Significant protocol deviation
- Clinical decision

The type of withdrawal and reason for withdrawal, if given, will be recorded in the CRF.

10.8 Definition of End of Study

The end of study is the point at which all the study data has been entered and queries resolved.

11. SAFETY REPORTING

We considered but decided to not record adverse events, except serious adverse events (see below section 11.1). It is hard to engage people who are in the control group (not a placebo) in recording adverse events, which seems an irrelevance to them, and these participants are also not attending appointments to collect such data. However, we will ask nurses in the intervention arm to record adverse events of special concernnamely episodes of hypoglycaemia or episodes of symptomatic hypotension that required outside assistance to manage, episodes of ketosis, or hospitalisation for international normalised ratio (INR) out of range in people on warfarin.

In addition, at 20 weeks, we will record serious adverse events for all patients, namely episodes of hospitalisation that were not planned at baseline, death or life-threatening event, illness or injury that resulted in permanent significant disability, or resulted in congenital abnormality. In the DiRECT trial, SAEs were less common in the intervention than control group. In our analysis, we will classify SAEs as diabetes-related (macrovascular or microvascular disease) or other. We will not prospectively record SAEs because this type of treatment is known to reduce the incidence of serious disease, and our retrospective recording will be sufficient to add to data on this.

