2. LAY SUMMARY

Type 2 diabetes (T2D) can be put into remission (achieving normal or near-normal blood glucose levels without medications) if treated with intensive weight loss support. Currently available evidence is that a very low-energy diet (about 800-900kcal per day) delivered using meal replacement products is the most effective way of achieving remission in primary care. However, about 75% of people offered a meal replacement programme turn it down, and low-carbohydrate low-energy diets could be an attractive alternative for many. Researchers at the University of Oxford developed a face-to-face low-carbohydrate, low-energy diet (DIAMOND) programme which achieved on average almost 10kg weight loss and normalisation of blood glucose in a 12-week feasibility study, and has now been taken to full trial.

The patients and healthcare professionals who took part in the DIAMOND study were keen to know whether the same results could be achieved using this dietary approach but when the behavioural component is provided through digital tools and remote support as an alternative to face-to-face appointments with a practice nurse. This has the potential for more frequent support without increasing the demand on the primary care workforce. Remotely-delivered interventions also offer more flexibility for the patient, without the need to attend a GP practice or physical location at a particular time. If effective, remote interventions could increase access and choice for patients who are keen to take part in a weight loss or remission programme. Encouraging data from other weight loss programmes show that a remote version can work just as well as a face-to-face version. Nevertheless, we want to test whether a

remote intervention of DIAMOND can achieve similar weight loss results as seen in the face-to-face version before rolling it out at scale.

Therefore, this proof of concept study aims to assess whether a remotely delivered behavioural support programme helps people follow a low-carbohydrate, low-energy diet (eDIAMOND) achieves clinically significant weight loss compared with no support or dietary advice.

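### Section 11 asks nurses to record the special-concern events, but coaches run all seven sessions, so events that do not lead to admission have no suitably placed recorder

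*Protocol*

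**What the plan says.** Section 11 decides against recording adverse events in general. It makes two exceptions: serious adverse events, for everyone, and four events of special concern, for the intervention arm. For the second group the instruction is that "we will ask nurses in the intervention arm to record adverse events". It names no other recorder and no time point for these events.

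The rest of the protocol describes an intervention without nurses:

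- The lay summary presents the behavioural component as "provided through digital tools and remote support as an alternative to face-to-face appointments with a practice nurse".
- Section 10.1 states that "the staff that deliver the remote coaching have a Level 3 qualification in health improvement/nutrition or similar", and section 10.6 confirms that the provider's health coaches deliver the sessions.
- The schedule in section 10.1 is "The programme will include remote coaching sessions at baseline, 2, 4, 8, 12, 16 and 20 weeks".
- On home monitoring, section 10.1 says "The coach will ask about the blood pressure, glucose and weight measures during the coaching sessions". It adds that the "hub coach will enter session data, which will include recordings of glucose and blood pressure readings" in an eCRF that the GP can view.
- Practice contact that is specific to the intervention arm is "1 additional telephone appointment with their GP or practice nurse, towards the start of the 12-week intervention period", for a medication review.
- Section 10.1 also says "there will be two-way communication between the hub coach and the GP practice".

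Section 10.3 adds a questionnaire link at week 12 and a practice visit at week 20, both for both arms.

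**The concern.** The named recorder does not fit the way this intervention is delivered. The coach speaks to the participant repeatedly through the 20 weeks and already asks about glucose and blood pressure, but is not asked to record these events. If nurses means practice nurses, they have little planned contact in which to learn of an event when it happens.

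Apart from serious adverse events, these are the only adverse-event data the trial plans to collect. Section 14.2 lists hypoglycaemia and hypotension among the main foreseeable risks of the diet, and section 15.1 says that no data monitoring committee will be convened. An event that was managed with help at home and never reached hospital could go unrecorded, or be recalled months later without a reliable date. A full trial would then be planned on counts that are probably too low.

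**Working it through.** No power or alpha figure enters this point. The check is a count of planned contacts against the named recorder, followed by a check of which events another rule already captures.

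**Step 1. Planned contacts after randomisation, intervention arm**

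| Contact | Who | Source |
|---|---|---|
| Coaching at baseline and weeks 2, 4, 8, 12, 16, 20 | Health coach | 10.1, 10.6 |
| One early medication call | GP or practice nurse | 10.1 |
| Week 12 | None (online questionnaire link) | 10.3.1 |
| Week-20 visit | Practice staff, type not named | 10.3.2 |

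- Coaching sessions: 7, of which nurses run 0.
- Coaching sessions from week 2 on: 7 - 1 = 6.
- Planned practice contacts: 1 call + 1 visit = 2. The call may be with the GP instead of a nurse.
- Planned practice contacts between the early call and the week-20 visit: 0. Coaches are scheduled at weeks 2, 4, 8, 12 and 16.

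That a nurse attends at week 20 is an inference. Section 9.5 speaks of patients telling the nurse their allocation, but section 10.3.2 names no staff type and section 9.4.2 allows a healthcare assistant at the baseline visit.

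**Step 2. Which of the four events are captured elsewhere**

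Section 11 records unplanned admissions at week 20 for all patients. Section 11.1 counts inpatient hospitalisation as serious, and section 11.2 has serious events recorded when the team learns of them.

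| Event in section 11 | Leads to admission | No admission |
|---|---|---|
| INR out of range | Captured as serious, both arms | Not part of the definition |
| Hypoglycaemia | Captured as serious, both arms | Rests on the nurse clause |
| Symptomatic hypotension | Captured as serious, both arms | Rests on the nurse clause |
| Ketosis | Captured as serious, both arms | Rests on the nurse clause |

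Three event types remain, in the form that does not lead to admission. The condition that outside help was needed plainly applies to hypotension and reads naturally as applying to hypoglycaemia too. Section 11.1 also lets some other medically important events be judged serious, which narrows the gap a little further.

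**Step 3. Does any other text assign the recording?**

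Coaches enter readings, follow eCRF prompts on what to tell the participant, and can contact the practice (10.1). The reason for a withdrawal is recorded (10.7). Neither provision tells anyone to record a special-concern event.

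**Step 4. Size of the proposed change**

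6 sessions from week 2 x 30 intervention participants (12.2) = at most 180 entries.

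**The case against.** The strongest defence is that nurses means practice nurses, and that the practice has several ways of learning about events. The GP can see the coach's entries, the eCRF prompts the coach to send participants to the practice, coach and practice can contact each other, and the self-monitoring instructions tell participants when to call. The practice also has its own notes. Nor is a low reading in itself one of the events, since outside help must have been needed. This stands as far as clinical care goes: the protocol does not leave participants unprotected. It does not answer the recording question, because none of these routes ends in someone being told to enter the event.

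Form-level detail may sit in the Data Management Plan or the Monitoring Plan, which are not at hand. That could supply a form or a time point. It would not correct the recorder that the protocol itself names.

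A reader might infer three stronger claims, and the documents do not support them:

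- *All four events go unrecorded, and nothing is known about controls.* INR admissions, and the other events when they lead to admission, are recorded as serious adverse events in both arms.
- *People who leave early have no further nurse contact.* The sample size does allow 30 - 21 = 9 per arm, but that is a margin for dropouts and is not linked to adverse events. Section 10.7 lists an intolerable event as a reason for stopping treatment, and those who stop are still offered the week-20 visit.
- *Leaving controls out is an error.* Both arms do attend at week 20, so asking controls is possible. But only the intervention arm receives home glucose and blood pressure monitors, so detection would differ by arm even with an identical question. Asking controls is an option, as is a tighter definition of ketosis.

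**Conclusion.** The point holds in a limited form. Section 11 gives the recording task to staff who run none of the seven sessions and whose planned contact after randomisation is at most one early call and one visit. Three event types are affected, and only where they do not lead to admission: hypoglycaemia and hypotension needing outside help, and ketosis. Their capture would rest mainly on week-20 recall or on ad hoc contact between coach and practice, so under-recording is likely. Its extent cannot be estimated, because the protocol gives no expected event rates.

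This rests on two readings: that nurses means practice nurses, and that a nurse is present at week 20, which is only implied. If a healthcare assistant does that visit, the mismatch is greater.

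The weight analysis, the sample size and the progression rule in section 12.3 are unaffected. This is a modest correction to safety recording that is worth considering. It is not evidence that participants are unsafe or that serious events will be missed.

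**What to change.** In section 11, replace the reference to nurses in the intervention arm with wording such as:

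> The coach asks about these events at each session from week 2 and records yes/no and date in the existing eCRF session form; the practice confirms them at the week-20 visit.

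The form already exists and the GP can already view it. No new visit or test is needed.

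The cost is one extra item per session (up to 180 entries), a short briefing so that coaches recognise the events as defined, and a protocol amendment if the sponsor judges one necessary.

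The main downside lies in interpretation. Intervention participants would be asked repeatedly and controls would not, so the report should state that these counts describe the intervention arm only and must not be compared with controls. The comparison between arms stays with serious adverse events, which are recorded for everyone.

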11.1. Definition of Serious Adverse Events

A serious adverse event is any untoward medical occurrence that:

• results in death

- is life-threatening (i.e., an event in which the participant was at risk of death at the time of the event; it does not refer to an event which hypothetically might have caused death if it were more severe).
- requires inpatient hospitalisation or prolongation of existing hospitalisation
- results in persistent or significant disability/incapacity
- consists of a congenital anomaly or birth defect.

Other 'important medical events' may also be considered a serious adverse event when, based upon appropriate medical judgement, the event may jeopardise the participant and may require medical or surgical intervention to prevent one of the outcomes listed above.

NOTE: The term "life-threatening" in the definition of "serious" refers to an event in which the participant was at risk of death at the time of the event; it does not refer to an event which hypothetically might have caused death if it were more severe.

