11.2. Reporting Procedures for Serious Adverse Events

The duration of the SAE recording period for each participant lasts from their enrolment on to the study, to their completion of the study. Any serious adverse event (SAE) occurring to a participant will be recorded at the time that the research team is made aware of the incident, and reported to the REC that gave a favourable opinion of the study where in the opinion of the Chief Investigator/clinically qualified member of the study team the event was 'related' (resulted from administration of any of the research procedures) and 'unexpected' in relation to those procedures. Reports of related and unexpected SAEs will be submitted within 15 working days of the Chief Investigator becoming aware of the event, using the HRA report of serious adverse event form, in accordance with HRA process.

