15. STUDY COMMITTEES

15.1 Trial Management Group

An independent trial steering committee (PSC) will provide oversight of all matters relating to participant safety and data quality. The PSC will include at least one independent clinician, an independent statistician and a participant representative. The PSC will be asked to review the trial protocol and will provide expert advice to the Project Management Group (PMG) on the trial progress.

A data monitoring and ethics committee (DMEC) will not be convened for this study.

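### Sections 11 and 11.2 give opposite rules on when serious adverse events are recorded, and sections 11 and 11.1 define them differently

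*Protocol*

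**What the plan says.** **When SAEs are recorded.** Protocol section 11 states that "at 20 weeks, we will record serious adverse events for all patients". It adds: "We will not prospectively record SAEs because this type of treatment is known to reduce the incidence of serious disease", and regards collection in retrospect as enough. Section 11.2 says: "The duration of the SAE recording period for each participant lasts from their enrolment on to the study, to their completion of the study", and that any SAE "will be recorded at the time that the research team is made aware of the incident". It then sets an expedited route: "Reports of related and unexpected SAEs will be submitted within 15 working days of the Chief Investigator becoming aware of the event".

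**What counts as an SAE.** Section 11 refers the reader to 11.1 and then gives its own list. Its disability criterion is "illness or injury that resulted in permanent significant disability". The criterion in 11.1 is "results in persistent or significant disability/incapacity".

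**What else is captured before week 20.** Section 11 asks nurses in the intervention arm to record four kinds of event of special concern: hypoglycaemia or symptomatic hypotension needing outside help, ketosis, and admission for an out-of-range INR. Section 10.1 schedules coaching at baseline and weeks 2, 4, 8, 12, 16 and 20. It also gives the GP sight of the session data and describes two-way contact between coach and practice. Control participants receive usual care only (section 10.2). Between baseline and week 20 the trial sends them one online food questionnaire, at week 12 (section 10.3.1).

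**Who oversees safety.** Section 15.1 gives this to a steering committee and says: "A data monitoring and ethics committee (DMEC) will not be convened for this study".

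**The concern.** A practice or coach who learns at week 3 that a participant has been admitted cannot tell from the protocol what to do. Under section 11 the event waits for the week-20 collection. Under 11.2 it is recorded once the research team knows of it. The 15-working-day clock starts only when the Chief Investigator becomes aware, and I found no instruction that coaches or practices should notify the study team of an SAE. The escalation route in section 10.1 runs between coach and practice.

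The second problem is the count itself. Section 11 plans to classify SAEs as diabetes-related or other. With two lists in force, the same event may be an SAE under one and not under the other, so the reported numbers depend on which section the recorder read.

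At stake are the timeliness of safety information reaching the steering committee, which is the only oversight body, and the consistency of the SAE table. The primary weight analysis is not affected.

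**Working it through.** The protocol gives no figure to reproduce here. The check is a comparison of the sections, followed by calendar arithmetic on the stated time points.

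**Step 1: recording rule.**

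| | Section 11 | Section 11.2 |
|---|---|---|
| Mode | retrospective, expressly not prospective | on the research team's awareness |
| Timing | once, at week 20 | from enrolment to completion |
| Expedited report | none mentioned | related and unexpected SAEs only, 15 working days from Chief Investigator awareness |

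As written, both rows on mode and timing cannot hold together.

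**Step 2: definition.**

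| Criterion | Section 11 | Section 11.1 |
|---|---|---|
| Death, life-threatening event, congenital anomaly | included | included |
| Hospital admission | only if unplanned at baseline | any inpatient admission or lengthened stay |
| Disability | permanent and significant | persistent or significant |
| Important medical events | not listed | may be included, on medical judgement |

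A significant but temporary disability meets the 11.1 wording and fails the section 11 wording. An important medical event without admission can be an SAE only under 11.1.

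**Step 3: longest delay if section 11 is followed.** Inputs: the follow-up visit is 20 weeks after randomisation (section 7), and the report is due 15 working days after awareness (section 11.2).

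- Event just after randomisation to first record: 20 weeks = 20 × 7 = 140 days.
- If the event is related and unexpected, add 15 working days = 15 / 5 = 3 weeks. Time to the ethics committee report: 20 + 3 = 23 weeks.
- The 11.2 period opens at enrolment, before randomisation, so the true maximum is slightly longer.

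**Step 4: longest gap between scheduled contacts, by arm.**

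- Intervention: sessions at 0, 2, 4, 8, 12, 16 and 20 weeks leave gaps of 2, 2, 4, 4, 4 and 4 weeks, so at most 4 weeks. Coaches are not told to ask about SAEs, so these are opportunities to learn of an event and do not guarantee it.
- Control: no visit between 0 and 20 weeks. The week-12 contact is a food questionnaire.

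Under 11.2 alone, awareness may therefore come within about 4 weeks in one arm and still wait until week 20 in the other.

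**The case against.** The strongest reply is that the sections can be read together: section 11 describes active collection for the analysis, and 11.2 covers events that the team happens to learn of sooner. That is sensible, but the protocol does not say it. Section 11 states flatly that recording is not prospective, so this reading is what the amended text should say.

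The reply on definitions is that 11.1 opens with untoward occurrences, and an admission planned before entry is hardly untoward. This largely disposes of the admission difference, though it should be stated once. The disability wording and the missing important medical events remain.

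It is also fair that interim capture is not nil. The events of special concern, the coaching sessions and the GP's continuing clinical responsibility all stand. Their limits are that they cover one arm and four event types. The recording is also assigned to nurses, whereas coaches deliver the sessions and the only additional GP or nurse contact described is one telephone appointment near the start.

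A reader might infer more than the protocol supports:

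- **That all safety oversight would lag by 20 weeks.** This holds only if section 11 prevails or nobody tells the team. Section 11.2 and the intervention-arm contacts point the other way.
- **That every SAE is reported within 15 working days.** Only related and unexpected SAEs are, counted from Chief Investigator awareness.
- **That 30 − 21 = 9 participants per arm would have no SAE record.** The 9 is the dropout allowance in section 12.2, not a forecast. Section 11 speaks of all patients and does not tie collection to attendance, although it names no source for those who do not attend.
- **That about 28 of 60 would be randomised before any SAE data exist.** Recruitment from 8 January to 31 October 2024 is 297 days, or 297 / 7 = 42.4 weeks, and 60 × 20 / 42.4 = 28.3. This assumes even accrual and randomisation from the first day, and it ignores the interim capture above. It does not measure the contradiction.

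**Conclusion.** Two contradictions stand on the text alone: the recording rule (section 11 against 11.2) and the SAE definition (section 11 against 11.1). If section 11 is followed, an early SAE could go unrecorded for up to 20 weeks, and a reportable one could reach the ethics committee after about 23. These are upper limits that assume an event soon after randomisation and no earlier awareness. That is most plausible in the control arm. The effect of the two definitions on the SAE count cannot be estimated, because the protocol gives no expected event rates.

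The sponsor's reason for not recording prospectively, that such treatment lowers serious disease, does not settle the matter. Section 14.2 itself lists hypoglycaemia, worsening retinopathy, hypotension and INR change as risks of the diet. The point should be corrected. It does not show that the trial lacks safety oversight.

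**What to change.** 1. Delete the section 11 sentence that rules out prospective recording.
2. State that any SAE known to a coach, a practice or the study team is notified and recorded when known, under 11.2, and made available to the steering committee.
3. Keep the week-20 collection in both arms and base the between-arm summary on it. Events learned of earlier will come more readily from the arm with coaching contacts, so they should not drive that comparison.
4. Use the 11.1 definition throughout, and say once whether admissions already planned at baseline are excluded.

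The cost is a rewording of section 11 and slight extra notification work for coaches and practices. Treatment, visits and sample size do not change. A week-20 check of GP records for all randomised participants, including non-attenders, would make ascertainment more even, but it is an optional extra that costs some practice time and is not needed to resolve the contradictions.
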